#### **3.3 Exploratory**

- a)
  - 1. EOM1.1: Frequency and descriptions of serious adverse events in pregnant women vaccinated with RIV4 versus IIV4 during the 42 days after vaccination.
  - 2. EOM1.2: Frequency and descriptions of serious adverse events in pregnant women vaccinated with RIV4 versus IIV4 during the study
- b)
  - 1. EOM2.1. Proportions of infants born small-for-gestational age after RIV4 versus IIV4 vaccination.
  - 2. EOM2.2: Proportion of pregnant women with clinical chorioamnionitis after RIV4 versus IIV4 vaccination.
  - 3. EOM2.3: Proportion of women with preeclampsia or eclampsia after RIV4 versus IIV4 vaccination.

c)

1. EOM3.1: Proportion of infants with medically-attended events through 90 days of life after maternal RIV4 versus IIV4 vaccination.
2. EOM3.2: Frequency and description of SAEs in infants through 90 days of life after maternal RIV4 versus IIV4 vaccination.
3. EOM3.3 Proportion of infants with neonatal death after maternal RIV4 versus IIV4 vaccination.

d)

1. EOM4.1: Proportion of pregnant women achieving seroconversion at day 29 after RIV4 versus IIV4 vaccination [a Hemagglutination Inhibition Assay (HAI) titer  $\geq 1:40$  at day 29 if the baseline titer is  $< 1:10$  or a minimum four-fold rise in HAI titer if the baseline titer is  $\geq 1:10$ ) for each influenza vaccine antigen].
2. EOM4.2: Proportion of pregnant women with a seroprotective HAI titer ( $\geq 1:40$ ) post-vaccination at day 29 after RIV4 versus IIV4 vaccination for each influenza vaccine antigen.
3. EOM4.3: The maternal geometric mean HAI titer (GMT) pre and post-vaccination at day 29 after RIV4 versus IIV4 for each influenza vaccine antigen and the post/pre-vaccination ratio.

e)

1. EOM5.1: Proportion of infants with cord blood seroprotective HAI titer ( $\geq 1:40$ ) for each influenza vaccine antigen after maternal RIV4 versus IIV4 vaccination.
2. EOM5.2: Infant cord blood geometric mean HAI titer (GMT) for each influenza vaccine antigen after maternal RIV4 versus IIV4 vaccination.
3. EOM5.3: Ratio of cord blood to maternal influenza antibody titers at time of delivery for each influenza vaccine antigen after maternal RIV4 versus IIV4 vaccination.

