#### **4.2 Laboratory**

**Serologic studies** – We will evaluate pre- and post-vaccination serologic responses in both IIV4 and RIV4 groups. IgG levels will be measured for the specific viral strains included in the 2019-2020 and 2020-2021 quadrivalent influenza vaccines using hemagglutination inhibition assays at the Duke Regional Biocontainment Laboratory (RBL) Virology Unit. Venous blood (approximately 15 mL of blood) will be collected from each participant before and 29 (-7 to +14) days after vaccination. At Duke, maternal and infant cord blood (approximately 15mL of blood each) collection will be performed at delivery for serological analysis in both RIV4 and IIV4 vaccination groups. At the other sites, these samples (maternal and cord blood) will be collected during delivery only if feasible for similar serological analysis. An assessment of placental antibody transfer (maternal:cord antibody ratio) will be determined.

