#### **6.3 Maternal Immunogenicity Population**

The Maternal Immunogenicity Population is a subset of the mITT Population that includes only pregnant women participants who received study vaccine, provide baseline and post-vaccination Visit 4 blood draws available for analysis within the protocol-defined time frame,

and with no major protocol violations affecting immunogenicity as determined by the study investigators.

The mITT Population is the primary analysis population for the safety and health outcomes analyses, with the PP Population as a confirmatory analysis population. The Immunogenicity Population is the primary analysis population for maternal immunogenicity outcomes (Exploratory Objectives 5); otherwise the mITT Population will be used for the Exploratory Objectives.

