The proportion of infants with medically-attended events through 90 days of life and the proportion of infants with neonatal death will be compared between the RIV4 group and the IIV4 group using an exact Mantel-Haenszel statistic (calculated in Proc Logistic in SAS) in a stratified analysis by site to control for the randomization blocks at the two-sided alpha 0.05 level. The proportion and 95% exact binomial confidence interval of SAEs in infants through 90 days of life, as well as the total number of events, will be presented by site, vaccine group, severity, and relatedness. Listings of these SAEs will also be presented. Non-overlapping confidence boundaries will be an indication of a statistical difference between the groups.

5. EO5: To compare maternal immune responses to influenza antigens and calculate the post and pre-vaccination ratio after RIV4 versus IIV4 vaccination.

The proportion of pregnant women achieving seroconversion at day 29 and the proportion pregnant women with a seroprotective HAI titer ( $\geq 1:40$ ) pre- and post-immunization at day 29 will be compared using a Mantel-Haenszel statistic in a stratified analysis by site to control for the randomization blocks at the two-sided alpha 0.05 level. The geometric mean HAI titer (GMT) pre- and post-immunization at day 29 after RIV4 versus IIV4 vaccination for each influenza vaccine antigen will be compared (within vaccine arm pre versus post and within timeframe RIV4 versus IIV4) using a regression model with the log transformed titer value at the two-sided alpha 0.05 level. The proportion and 95% exact binomial confidence interval will also be presented in tabular format for each group. The Immunogenicity Population is the primary analysis population. The Maternal Immunogenicity Population is the primary analysis population.

6. EO6: To compare cord blood antibody levels for influenza antigens after RIV4 versus IIV4 vaccination.

The proportion of infants with cord blood seroprotective HAI titer will be compared using a Mantel-Haenszel statistic in a stratified analysis by site to control for the randomization blocks at the two-sided alpha 0.05 level. Infant cord blood geometric mean HAI titer (GMT) for each influenza vaccine antigen will be compared using a regression model with the log transformed titer value at the two-sided alpha 0.05 level.

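### SAP 8.3 EO5 does not say how paired titres are modelled, names no baseline adjustment for the day-29 arm contrast, gives no between-arm estimate for the listed post/pre ratio, and tests the arms before vaccination (minor, exploratory)

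*SAP*

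**What the plan says.** The maternal immune-response objective is EO5 in SAP 8.3 and Exploratory Objective 4 in Protocol 7.3.11. Both give the same method for GMTs: "within vaccine arm pre versus post and within timeframe RIV4 versus IIV4) using a regression model with the log transformed titer value", at the two-sided 0.05 level. Nothing further is said about the model. Neither document names a subject effect, a paired test, a repeated-measures covariance or a baseline covariate.

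The data are paired. Under SAP 4.2, blood "will be collected from each participant before and 29 (-7 to +14) days after vaccination". Under SAP 6.3, the Maternal Immunogenicity Population is limited to women who "provide baseline and post-vaccination Visit 4 blood draws available for analysis within the protocol-defined time frame".

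The fold-rise is a listed outcome. EOM4.3 in SAP 3.3 covers the GMT before and after vaccination "for each influenza vaccine antigen and the post/pre-vaccination ratio". The EO5 objective reads "To compare maternal immune responses to influenza antigens and calculate the post and pre-vaccination ratio after RIV4 versus IIV4 vaccination", but no interval or between-arm method follows for that ratio. Seroconversion, which includes "a minimum four-fold rise in HAI titer if the baseline titer is" at or above 1:10, is compared between arms, as is seroprotection; these proportions "will be compared using a Mantel-Haenszel statistic in a stratified analysis by site". EO5 makes the seroprotection comparison both before and after vaccination, although EOM4.2 lists only the post-vaccination proportion.

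**The concern.** There are four gaps, all in the same few lines.

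- The pre/post contrast within an arm uses two values from each woman, and the stated method does not say how their correlation enters. A programmer could fit independent errors and still comply.
- The RIV4 versus IIV4 contrast at day 29 is the randomised comparison of response. The plan does not say that it uses the baseline titre, which every woman in this population has.
- The two stated GMT contrasts do not include a between-arm comparison of the rise, so the ratio in EOM4.3 has no estimate of vaccine difference. By contrast, EO6 gives the cord-to-maternal ratio a 95% CI and a rule for reading it.
- The within-timeframe contrast covers the pre-vaccination time point, so randomised arms are tested against each other before any vaccine is given.

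At stake are precision and a pre-specified model for an exploratory result. No primary or secondary conclusion depends on it.

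**Working it through.** **Plan's own figure.** No design figure is given for any titre endpoint. The one power statement that can be checked is for the primary endpoint (SAP 4.3: 15% in both arms, 10% margin, one-sided 0.025, 204 per arm, about 81%). SE = √(2 × 0.15 × 0.85 / 204) = 0.0354, and power = Φ(0.10/0.0354 − 1.96) = 80.7%. Exact enumeration with an unstratified Newcombe interval gives 80.4%. The figure reproduces, and this point does not touch it.

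**Inputs for EO5.** Two draws per woman, both required (SAP 4.2 and 6.3), and two-sided 0.05 (SAP 5.2). The within-woman correlation ρ of log titre and the SDs are not in the documents. Assumed here: ρ = 0.3, 0.5, 0.7, with equal SD σ before and after vaccination. The number of women n per arm cancels from every ratio below.

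**Within-arm rise.** The variance of the mean of (post − pre) is 2σ²(1 − ρ)/n when pairing is used and 2σ²/n when independence is assumed. The SE ratio is therefore 1/√(1 − ρ). A nominal 0.05 test would run at 2[1 − Φ(1.96/√(1 − ρ))].

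**Between-arm contrast.** With one day-29 value per woman, the unadjusted contrast has variance 2σ²/n, whatever is assumed about pairing. An unadjusted change score has 4σ²(1 − ρ)/n, an SE ratio of √(2(1 − ρ)). Day-29 titre adjusted for baseline has 2σ²(1 − ρ²)/n, an SE ratio of √(1 − ρ²).

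| Assumed ρ | Within-arm SE, independence / paired | Level of nominal 0.05 test | Arm contrast: change score / day-29 only | Arm contrast: baseline-adjusted / day-29 only |
|---|---|---|---|---|
| 0.3 | 1.20 | 0.019 | 1.18 | 0.95 |
| 0.5 | 1.41 | 0.006 | 1.00 | 0.87 |
| 0.7 | 1.83 | 0.0004 | 0.77 | 0.71 |

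A simulation of the within-arm test (204 women, 5,000 runs) rejected at 0.019, 0.004 and 0.0002 under independence, and at 0.053, 0.049 and 0.054 with pairing.

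**Unequal SDs.** If the post/pre SD ratio is k, the within-arm inflation is √[(1 + k²)/(1 + k² − 2kρ)]. For k = 2 and ρ = 0.5 this is √(5/3) = 1.29, against 1.41 for equal SDs. The within-arm column is thus the largest inflation for each ρ.

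**The listed ratio.** With baseline log titre in the model, the arm coefficient is the same whether the response is day-29 log titre or the change from baseline. The adjusted RIV4:IIV4 ratio therefore also serves as the between-arm ratio of fold-rises for EOM4.3.

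**Baseline tests.** For GMT on four antigens, 1 − 0.95⁴ = 18.5% chance of at least one p < 0.05 when no difference exists, if the four were independent, and less if they are correlated.

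**The case against.** A reader might infer that the plan fits an ordinary regression that treats the two titres as unrelated, so that its pre/post intervals are wrong. The documents do not support that. They leave the model type open, and a repeated-measures regression with arm and time would also comply. The inflation in the table is conditional on a choice that the text permits but does not make. Even then, intervals would be too wide and tests too strict, so no false claim of a rise would follow, and the day-29 arm contrast would be unaffected.

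A reader might also infer that the comparison of response between vaccines is missing. It is not. Seroconversion and day-29 GMT are both compared between arms, and under randomisation the day-29 GMT ratio estimates the same vaccine effect as the ratio of fold-rises. EO5 asks only that the post/pre ratio be calculated. What stands is that seroconversion is a dichotomised and separately listed outcome, and that the continuous ratio in EOM4.3 has no interval or between-arm estimate.

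Nor is a simple change score an automatic improvement: below ρ = 0.5 it is less precise than the contrast already planned. On the baseline tests, seroprotection is a cut of the same titre, so counting it as a further independent set of tests would overstate the chance of a false signal. Inspecting baseline titres by arm is reasonable, but description is enough for that.

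**Conclusion.** The point holds as a minor, cost-free improvement to an exploratory objective. EO5 and Protocol 7.3.11 leave the within-woman correlation unaddressed, name no baseline adjustment for the randomised contrast, give the EOM4.3 ratio no between-arm estimate or CI, and test the arms before vaccination.

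The useful gain is in the day-29 arm contrast. Adjusting for baseline reduces its standard error by about 5%, 13% or 29% at ρ of 0.3, 0.5 or 0.7. The possible loss in the within-arm intervals is conservative and arises only if independence is assumed. Both sizes rest on assumed correlations and equal SDs, because the documents give neither. The documents show an incomplete specification; they do not show a wrong analysis.

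**What to change.** In SAP 8.3 EO5 and Protocol 7.3.11, state for each antigen:

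1. Within each arm, the geometric mean fold-rise with a 95% CI from the paired differences in log titre.
2. Between arms, the RIV4:IIV4 ratio with 95% CI from day-29 log titre, adjusted for baseline log titre and site. A repeated-measures model with within-woman covariance and a common baseline mean is an alternative. Report this as the between-arm result for EOM4.3, and do not use an unadjusted change score.
3. Pre-vaccination GMT and seroprotection by arm, shown descriptively without between-arm tests.

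The cost is a few lines of wording and routine code. The samples, visits and analysis population do not change.

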7.3.16 Further analysis

Prior to the second season of enrollment, randomization was stratified by gestational age (<20 weeks versus 20-34 weeks) and by site. Stratification by gestational age was removed from Version 2.1 due to an error in the randomization schema noted after the first season. The overall randomization to RIV4 vs IIV4 was maintained but the gestational age stratification was unbalanced due to the error.

If the error in stratification by gestational age results in an imbalance in gestational age between the treatment groups, evaluation of secondary outcomes by treatment group will be done using gestational age as a covariate if specified analyses can adjust for this factor. To have reasonable results, each cell count needs to be 5 or greater.

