#### **4.4 Randomization**

Participants will be randomized (1:1) to receive either RIV4 (Flublok® quadrivalent recombinant influenza vaccine) or IIV4 (quadrivalent inactivated influenza vaccine) using a permuted block randomization scheme stratified by study site (Duke, Cincinnati, Boston). The project statistician will generate permuted block randomization schemes which will be uploaded to REDCap. The randomization schedule will not be available to the study staff, so the next randomization allocation will not be known before randomization occurs. Following confirmation of study eligibility criteria during Visit 1, participant randomization will be through REDCap with treatment allocation recorded on the case report form (CRF).

In the event that REDCap is unavailable, manual randomization will occur through the use of envelopes. The project statistician will prepare 20 envelopes per gestational age group per site (total of 40 per site) that will use the same randomization strategy as the primary scheme embedded in REDCap. When an unblinded team member is informed of the gestational age group, he/she will pull the next envelope in order. In order to capture the allocation per subject, a separate form in REDCap will be used by the unblinded personnel to add the assignment. A log will need to be kept at the site capturing these instances.

We had planned to have gestational age as a stratification factor for randomization (<20 weeks,  $\geq$  20 weeks). Unfortunately, the setup in REDCap only drew from the <20 weeks randomization block. The benefits for randomization have been maintained, and we will evaluate secondary outcomes by site and gestational age to determine if specified analyses can adjust for this factor. The cell counts need to be 5 or greater to have reasonable results.

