#### **5.2 Analytic Issues**

There are three study sites participating in the study and analysis of the primary objective will be stratified by site (Duke, Boston, Cincinnati) to account for this unit of randomization. All objectives will be stratified by site when applicable. There is one primary objective being evaluated, using a noninferiority hypothesis at the one-sided alpha 0.025 level. Otherwise, the alpha level will be set at two-sided alpha 0.05 for the secondary objectives and all exploratory objectives.

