## 7 BASELINE DATA AND FLOW CHART

### 7.1 Presentation of Baseline Data

The following baseline information will be presented by treatment group, age, ethnicity, race and tobacco, marijuana or other substance use, gestational age at vaccination, study enrollment site, and influenza season of enrollment. Summary statistics (e.g., mean, standard deviation, median) will be presented for continuous variables. Categorical variables will be described with frequencies and percentages. Specific medical issues (i.e., hypertension, diabetes, and prior preterm birth) will also be presented.

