## **10 FURTHER ANALYSIS**

If the error in stratification by gestational age results in an imbalance in gestational age between the treatment groups, evaluation of secondary outcomes by treatment group will be done using gestational age as a covariate if specified analyses can adjust for this factor. To have reasonable results, each cell count needs to be 5 or greater.

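### The cord-blood titre regression prespecifies no adjustment for gestational age at vaccination, which largely sets when the cord sample is taken relative to vaccination

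*SAP*

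**What the plan says.** The cord-blood objective is EO6 in SAP 8.3 and EO5 in Protocol 7.3.12. SAP 8.3 says that infant "cord blood geometric mean HAI titer (GMT) for each influenza vaccine antigen will be compared using a regression model with the log transformed titer". The test is two-sided at 0.05. Neither document lists a covariate for this model.

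Three other places could supply one:

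- SAP 5.2 adds site and nothing else: "All objectives will be stratified by site when applicable".
- SAP 10, matched by Protocol 7.3.16, deals with the failed stratification. If gestational age turns out to be imbalanced between the arms, "evaluation of secondary outcomes by treatment group will be done using gestational age as a covariate if specified analyses can adjust for this factor". SAP 4.4 also mentions only secondary outcomes.
- SAP 7.1 has the baseline table show "gestational age at vaccination, study enrollment site, and influenza season of enrollment" by treatment group, so the variable is on file for the randomised women.

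On the history, Protocol 7.3.16 records that before the second season "randomization was stratified by gestational age (<20 weeks versus 20-34 weeks) and by site". SAP 4.4 explains the failure: "Unfortunately, the setup in REDCap only drew from the <20 weeks randomization block". The factor was then dropped.

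On timing, Protocol 4.1 admits women vaccinated at any gestation up to 34 weeks 0 days. Protocol 3.2.1 and Visit 6 put the cord sample at delivery, routinely at one site and if feasible at the other two.

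**The concern.** The maternal response is measured at a fixed point, Day 29. The cord sample has no fixed point: its distance from vaccination is whatever remains of the pregnancy. Women within one arm may therefore be sampled a few weeks or more than half a year after vaccination. If titre changes over that span, the change becomes residual noise in the comparison of arms. Any chance difference between arms in vaccination timing also becomes part of the estimated geometric mean titre (GMT) ratio.

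The plan accepts gestational age as a covariate, and once stratified on it, yet its adjustment rule stops at the secondary outcomes. It leaves out the outcome whose sampling time gestational age directly governs. At stake are some precision in an exploratory comparison and protection against a chance imbalance in a subset that the baseline table is not stated to describe separately.

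**Working it through.** **1. The plan's own figure.** No power or precision is stated for cord blood. The only power figure is for the primary endpoint (SAP 4.3: 15% event rate, 10-point margin, 204 per arm, one-sided 0.025, about 81%). It reproduces: SE = sqrt(2 × 0.15 × 0.85 / 204) = 0.0354, and power = Φ(0.10/0.0354 − 1.96) = 80.7%. It says nothing about titres.

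**2. Which rule reaches the cord model.**

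| Source | Covers | Reaches the cord regression? |
|---|---|---|
| SAP 8.3 EO6 / Protocol 7.3.12 | log-titre regression | yes, but names no covariate |
| SAP 5.2 | all objectives, site only | site only |
| SAP 4.4 | secondary outcomes | no |
| SAP 10 / Protocol 7.3.16 | secondary outcomes, if imbalance | no |

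**3. How far gestational age sets the interval.** Interval = gestation at delivery − gestation at vaccination.

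| Vaccinated at | Delivery at 37 weeks | Delivery at 40 weeks |
|---|---|---|
| 34w0d | 3 weeks | 6 weeks |
| 20w0d | 17 weeks | 20 weeks |
| 8w0d | 29 weeks | 32 weeks |

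Treat the two gestations as independent. The share of interval variance due to gestation at vaccination is then V/(V + D), where V and D are the variances at vaccination and at delivery. The distributions are assumptions, because the documents give none. For vaccination uniform over 6–34 weeks, V = 28²/12 = 65.3. With a delivery SD of 2 weeks, D = 4 and the share is 65.3/69.3 = 94%. Over uniform ranges of 6–34 or 12–34 weeks and delivery SDs of 1.5 to 2.5 weeks, the share is 87–97%. If all women were vaccinated at 20–34 weeks, it is 72–88%.

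**4. Precision gain.** Adjustment multiplies the SE by sqrt(1 − R²), where R² is the share of log-titre variance that gestational age explains. R² is not in the documents, so a range is shown.

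| R² | SE factor | SE reduction | Equivalent sample, 1/(1 − R²) |
|---|---|---|---|
| 0.05 | 0.975 | 2.5% | 1.05 × |
| 0.10 | 0.949 | 5.1% | 1.11 × |
| 0.25 | 0.866 | 13.4% | 1.33 × |

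As an illustration, assume 100 cord samples per arm, an SD of 2 log2 units and a true GMT ratio of 1.68. Power is 75.5% unadjusted, 77.7% at R² = 0.05, 79.8% at 0.10 and 84.2% at 0.20.

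**5. Chance imbalance.** With an assumed gestational-age SD of 8.1 weeks, the arm difference in mean gestational age has SD 8.1 × sqrt(2/n): 1.48, 1.15 and 0.80 weeks at 60, 100 and 204 per arm. If titre changes by a factor f per 20 weeks, a 1.96-SD imbalance multiplies the GMT ratio by f^(1.96 × SD/20). At 100 per arm this is 1.047 for f = 1.5, 1.081 for f = 2 and 1.168 for f = 4. Across 60 to 204 per arm the shift is 3–6%, 6–11% and 12–22% respectively.

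**6. Validity.** A simulation of 20,000 null trials (100 per arm, titre SD 2 log2 units, gestational age uniform over 6–34 weeks) gave the unadjusted test a type I error of 5.1% for f = 2 and 5.0% for f = 4. Among trials with an imbalance beyond 1.96 SD, it was 7.6% and 13.8%, against 4.3% and 4.4% with adjustment.

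**The case against.** The strongest defence is that nothing here is an error. Treatment was randomised, and SAP 4.4 says the benefits of randomisation were kept. The unadjusted test holds its level on average, and the endpoint is exploratory. The SAP says only that a regression will be used, so gestational age is unstated, not excluded. All of that stands.

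It is also fair that the documents never say cord titre depends on time since vaccination. They show only that the interval varies. The precision gain therefore rests on an assumed relation and could be small. That relation might not be a straight line: titres could be lower both soon after vaccination and long after it, and a single linear term would then recover little. This objection shapes the fix.

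The stratification argument has limits too. Balancing all 430 women on two gestational-age bands would not have guaranteed balance in a cord subset selected by feasibility, nor in gestational age within a band. The overall baseline table would show a gross imbalance, though not necessarily one confined to the cord subset.

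Four stronger readings are tempting but unsupported:

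- A reader might infer that the REDCap error biases the comparison. Protocol 7.3.16 says the overall allocation was maintained, and no document shows that the arms differ.
- A reader might infer that an imbalance also carries directly into the cord:maternal ratio. Both samples come from the same delivery, so a timing effect common to them cancels.
- A reader might infer that this is the analysis with the fewest samples. No cord count is given, and spontaneous abortion is also analysed in a subset.
- A reader might infer that many cord samples precede the Day 29 response point. Vaccination at 34w0d does put Day 29 at 38w0d. However, SAP 8.3 assigns EO6 to the Immunogenicity Population, which requires a Visit 4 draw and so mostly removes such women. SAP 6.3 would instead place this objective in the mITT population, where they could remain.

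**Conclusion.** The gap is real and minor. No passage brings gestational age at vaccination into the cord log-titre model, although that variable accounts for most of the variation in time from vaccination to sampling under every distribution tried. The planned comparison is valid; what may be lost is precision and protection against chance imbalance.

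The size cannot be fixed from the documents. The SE would fall by about 2.5% at R² 0.05, 5% at 0.10 and 13% at 0.25. An unlucky imbalance would move the GMT ratio by a few percent for a shallow titre gradient, and by 12–22% only under an assumed four-fold change per 20 weeks. These figures rest on assumed gestational-age distributions, titre SD, sample counts and gradients. The conclusion applies to the cord GMT comparison and does not extend to the cord:maternal ratio.

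**What to change.** In SAP 8.3 EO6 and Protocol 7.3.12, state that log cord titre will be regressed on vaccine arm, site and gestational age at vaccination (continuous, in weeks), whether or not an imbalance is observed. State in advance how a non-linear relation will be checked or allowed for, for example with a quadratic term, so that the form is not chosen after seeing the arm comparison.

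Use gestational age at vaccination and not the vaccination-to-delivery interval. Delivery timing arises after randomisation, and preterm birth is part of the primary endpoint. Using the same model for the log cord:maternal ratio is optional.

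The cost is a change of wording in two places and one degree of freedom per model for the linear term, or one more with a quadratic. No new data are needed, since the variable is already collected and tabulated by arm.
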